## **15. STUDY POPULATION**

The study includes prospectively defined study populations.

The Intent-to-Treat (ITT) population will include all subjects who received the randomized study treatment. The modified ITT (mITT) population will include the ITT population with at least one post-randomization efficacy observation. The Per-Protocol (PP) population will also exclude mITT subjects with a major protocol deviation, e.g. ineligibility, unreliable MADRS-10 scoring, proscribed treatment. The Safety Population will include all subjects as treated.

The mITT population will be used for the primary efficacy analyses. If <5% are to be excluded from the mITT population, then the analysis will not be performed for the PP population.

Every effort will be made to encourage subjects to comply with the procedures and the assessments. Protocol violations will be reviewed in real time and prospective rules will be set for exclusions from the PP population. A Biostatistics Data Review Meeting (BDRM) will be held to identify all major protocol deviations prior to database lock inclusive of any case exclusions from the mITT and PP population as well as to manage any efficacy data following proscribed treatments.

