16.2 Study Populations

The study includes prospectively defined study populations. The Intent to Treat (ITT) population will include all participants who received at least one dose of the oral treatment and had any post–randomization efficacy assessments. The modified ITT (mITT) population will include the ITT population with at least one post-baseline efficacy observation; the mITT population will also exclude subjects with a major protocol deviation, e.g. ineligibility, unreliable MADRS-10 scoring, proscribed treatment. The Per Protocol (PP) population will include the subset of ITT participants who were eligible, who have any post–randomization efficacy assessments within one day of scheduled visits through Day 7 and within three days of scheduled visits through Day 42, and who had no major protocol violations. The Safety population will include all participants as treated with study treatment and with any post–randomization safety data.

The mITT population will be used for the primary analyses for efficacy. If <5 percent are to be excluded from the ITT population, then the analysis will not be performed for the PP population.

Protocol violations will be reviewed in real time and prospective rules will be set for exclusions from the PP population. A Biostatistics Data Review Meeting (BDRM) will be held to identify all major protocol deviations prior to database lock inclusive of any case exclusions from the mITT and PP population as well as to censor any efficacy data following proscribed treatments.

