#### 19.4 Estimand Structure

Analyses will be conducted in accordance with ICH E9 (R1) analysis principles as summarized below.

Primary scientific question of interest	The primary study hypothesis is that treatment with NRX-101 is superior to lurasidone in improving symptoms of depression as measured by the MADRS over 6 weeks of treatment. The null hypothesis for the primary endpoint is the mean change from baseline of MADRS-10 for NRX-101 is the same as lurasidone while the alternative hypothesis is that the mean change from baseline of MADRS-10 is larger than the mean change from baseline of MADRS-10 for lurasidone. Baseline is defined as MADRS-10 score at Visit 2 (randomization).
Target population	The mITT population will be the primary analysis population. The mITT population is defined through appropriate inclusion/exclusion criteria as specified in the protocol and blinded BDRM decisions.
Treatment of interest	NRX-101
Outcome Variables	MADRS-10 (and C-SSRS) will be recorded as audio files and reviewed by central master-raters with any non-congruent subject-visits from any site with >10% non-congruent scores sent to a qualified independent adjudicator to be considered as the subject-visit primary study endpoint.
Summary Measure	The contrast-estimated MADRS-10 Week 6 MMRM will use all post-randomization data with LOCF in the mITT population excluding all outcomes after BDRM-approved exclusions. The model will include treatment and the following four baseline covariates in addition to baseline MADRS-10: (1) sex, (2) mood stabilizer use, (3) anti-psychotic use, and (4) evidence of suicide event in their lifetime. The model will include treatment group, study visit, the interaction between study visit and treatment group, baseline MADRS-10, and the four baseline covariates as fixed effects. An unstructured error structure will be assumed.
Intercurrent Events	A BDRM will adjudicate all intercurrent events which may redact outcomes after disqualifying events; these intercurrent events may represent major protocol deviations.

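### SAP 15 and 19.4 leave the primary mITT set open to case exclusions by the data review meeting, which contradicts the SAP's own mITT definition and has no prospective rule

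*SAP*

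**What the plan says.** SAP 15 names the primary set: "The mITT population will be used for the primary efficacy analyses". It defines that set by data availability alone: "The modified ITT (mITT) population will include the ITT population with at least one post-randomization efficacy observation". The ITT set on which this builds is everyone who received randomized treatment. Deviations are handled one level down: "The Per-Protocol (PP) population will also exclude mITT subjects with a major protocol deviation, e.g. ineligibility, unreliable MADRS-10 scoring, proscribed treatment". The SAP synopsis, under Analysis Sets, draws the same division.

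The last paragraph of SAP 15 departs from this. It says that "prospective rules will be set for exclusions from the PP population", and then has the BDRM "identify all major protocol deviations prior to database lock inclusive of any case exclusions from the mITT and PP population". No rule for mITT exclusions is given or promised.

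The target-population row of SAP 19.4 states: "The mITT population is defined through appropriate inclusion/exclusion criteria as specified in the protocol and blinded BDRM decisions". The intercurrent-event row adds: "A BDRM will adjudicate all intercurrent events which may redact outcomes after disqualifying events". The summary-measure row drops outcomes that follow BDRM-approved exclusions and applies LOCF.

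Protocol 16.2 has a different mITT: "the mITT population will also exclude subjects with a major protocol deviation". SAP 13 says that the SAP governs where the two documents disagree.

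**The concern.** A participant can meet the SAP 15 definition of mITT and still be taken out of mITT by a meeting that has no written criteria for doing so. SAP 13 does not resolve this, because the conflict is within the SAP: one part of section 15 against another, and section 15 against 19.4.

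What is at stake is the randomized comparison for the primary endpoint. Two of the deviation types that SAP 15 lists as examples arise after randomization and can depend on how the patient is doing. Proscribed treatment is the clearest. The treatment-failure definition in SAP 16.3 counts any change in baseline antidepressant, mood stabilizer or antipsychotic as a failure, and SAP Appendix 1 permits no antidepressant dose change during the study. The same event could make a patient a failure on a secondary endpoint and a candidate for removal from the primary analysis. Unreliable MADRS scoring concerns the outcome itself, for which SAP 17.1.1 already provides central review and adjudication.

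Blinded review before database lock prevents choosing cases by arm. It does not prevent bias when the reason for exclusion is itself a consequence of treatment.

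**Working it through.** **Inputs.** From SAP 18.2 and the sample-size row of the SAP synopsis: 37 per arm, SD 13.4, difference 8.85 points (effect size 0.66), two-sided 5%, effect size 0.462 for p = 0.05, and illustrative mean changes of -16 (NRX-101) and -10 (lurasidone). The documents give no exclusion rate and no dropout allowance, so every exclusion count below is assumed.

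**1. The plan's own figures reproduce.**
- Effect size: 8.85 / 13.4 = 0.660.
- Power of a two-sample t-test, from the noncentral t with 72 df and noncentrality 0.66 × √(37/2): 80.0% (normal approximation 81.1%). The plan states 80%.
- Smallest significant effect size: t(0.975, 72 df) × √(2/37) = 0.463. The plan states 0.462, which is 0.462 × 13.4 = 6.2 points.

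**2. Whole-case removal of non-improvers.** If k patients with change 0 leave an arm of 37 whose mean is m, the mean of those remaining is m × 37/(37 − k). With k = 3:
- NRX-101: -16 × 37/34 = -17.41, a shift of 1.41 points (1.41/13.4 = 0.11 SD).
- Lurasidone: -10 × 37/34 = -10.88, a shift of 0.88 points.

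| Removed | Change in the difference between arms |
|---|---|
| 3 from NRX-101 only | 1.41 points in favour of NRX-101 |
| 3 from each arm | 1.41 − 0.88 = 0.53 points (0.04 SD) in favour of NRX-101 |
| 3 from lurasidone only | 0.88 points against NRX-101 |

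**3. Type I error, NRX-101 arm only, no true effect** (simulation, 40,000 trials per row, normal outcomes, SD 13.4, t-test).

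| Removed | k worst outcomes: shift, error | k at random from the worse half: shift, error |
|---|---|---|
| 1 | 0.8 points, 6.2% | 0.3 points, 4.8% |
| 2 | 1.5 points, 8.5% | 0.6 points, 5.2% |
| 3 | 2.1 points, 11.8% | 0.9 points, 5.7% |
| 4 | 2.7 points, 15.6% | 1.2 points, 6.3% |

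The middle column is an extreme bound. The right-hand column is a milder link between outcome and exclusion.

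**4. Power under non-informative loss, split equally.** With 4 removed (4/74 = 5.4%, 35 per arm), power is 77.7%. With 8 removed (8/74 = 10.8%, 33 per arm), it is 75.2%. This is a separate cost from the bias in steps 2 and 3.

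**The case against.** Much of the SAP points towards keeping deviators in mITT. Its PP definition removes deviators from mITT, so they must be in mITT to begin with. The rule that skips the PP analysis when fewer than 5% would be excluded from mITT also makes sense only if mITT still contains them. The BDRM sentence has a harmless reading: the meeting confirms who fails each set's definition, which for mITT means having no qualifying observation. Decisions are described as blinded and come before lock.

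These points show what the authors probably intended. They do not cancel a sentence that names mITT among the sets open to case exclusion, or a row in 19.4 that makes membership depend on BDRM decisions.

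Three stronger readings are tempting, and the documents support none of them.

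- A reader might infer that the SAP adopts the mITT definition of Protocol 16.2. The row in 19.4 refers to inclusion and exclusion criteria, which are the protocol's own headings for eligibility (8.1 and 8.2), and it does not cite 16.2. It can be read either way; that ambiguity is the defect.
- A reader might infer that the primary analysis becomes nearly the PP analysis. That would follow only if the BDRM removed essentially every deviator from mITT, which the SAP does not say.
- A reader might take 1.4 points as the expected bias. It requires whole patients to be deleted, all from one arm and all with zero change. For proscribed treatment, SAP 15 speaks of managing the later efficacy data, and 19.4 of redacting later outcomes with LOCF. Under that route a patient at change 0 before the event stays in at 0, and the shift from removal is nil.

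SAP 20.1 also mentions a supportive multiple-imputation presentation in ITT. The same paragraph names mITT as the imputation set, so it is not a clear check on an unexcluded population.

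**Conclusion.** The point holds as an inconsistency inside the SAP about who is in the primary analysis. SAP 15 and 19.4 permit removal of treated participants with outcome data from mITT, without prospective criteria and for reasons that can be related to outcome. The BDRM clause is enough for this, whichever way the protocol reference in 19.4 is read.

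The size cannot be fixed from the documents. With 3 assumed zero-change removals per affected arm, the difference moves by between 1.4 points in favour of NRX-101 and 0.9 points against it, and by about 0.5 points if both arms lose 3, compared with the 6.2 points needed for p = 0.05. Type I error could stay close to 5% or, in the extreme one-arm case, exceed 10%. The effect may be small in practice, but with 37 per arm a few discretionary removals can matter. This should be corrected before database lock.

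**What to change.** 1. In SAP 15 and 19.4, give one definition of mITT: all randomized, treated participants with at least one post-randomization MADRS, analysed as randomized.
2. In the BDRM sentence of SAP 15, delete the reference to mITT so that case exclusions concern PP only. In the target-population row of 19.4, delete the clause that ties mITT to the protocol and to BDRM decisions.
3. Limit the BDRM's role for mITT to confirming who lacks a qualifying observation. Apply deviation-based case exclusions to PP only.
4. Because 19.4 would still let the BDRM redact outcomes after disqualifying events, add a sensitivity analysis of the same mITT set using all observed MADRS data without BDRM redaction.

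The cost is SAP wording and one additional analysis of data already collected. The PP analysis remains available to show the result without deviators, subject to the SAP's own 5% rule.

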## 16. HYPOTHESIS TESTS

### 16.1 Treatment Comparisons

In order to preserve the Type 1 error associated with multiple endpoints (per FDA guidance), all efficacy endpoints will be evaluated in this pre-defined order: (1) MADRS through Week 6. Each will be hypothesis testing driven.

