## 7.2 Secondary Efficacy Objectives

- To test the hypothesis that treatment with NRX-101 is superior to standard of care (lurasidone) in reducing suicidal ideation (MADRS item 10).
- To test the hypothesis that treatment with NRX-101 is superior to lurasidone in the change from baseline to Day 14 in MADRS total score.
- To test the hypothesis that treatment with NRX-101 is superior to lurasidone in reducing the frequency of suicidal thoughts, suicidality and risk (SIBAT Module 7).
- To test the hypothesis that NRX-101 is superior to lurasidone in reducing suicidal ideation or behavior as measured by the Clinical Global Impression of Severity of Suicidality Scale (CGI-SS)
- To test the hypothesis that NRX-101 is superior to lurasidone in time to treatment failure as defined as: study discontinuation due to adverse events; psychiatric hospitalization; or requiring a change in antidepressant treatment.
- To test the hypothesis that treatment with NRX-101 is superior to treatment with lurasidone in the subgroup of participants recently (i.e. within two weeks of enrollment) treated with approved medications for bipolar depression (olanzapine/fluoxetine, quetiapine, cariprazine, lumateprazole, or lurasidone).
- To test the hypothesis that treatment with NRX-101 is superior to treatment with lurasidone in the subgroup of participants recently (i.e. within two weeks of enrollment) treated with approved medications for bipolar depression.
- To further test the hypothesis that treatment with NRX-101 is superior to treatment with lurasidone in the subgroup of participants recently (i.e. within two weeks of enrollment) treated with any 5-HT2A agonist for the primary efficacy endpoint.

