### 18.3 Hierarchical Testing Strategy

The secondary efficacy hypotheses will also be evaluated using a hierarchical testing strategy where testing continues as long as two-sided  $p<0.05$  is reached. The first such hypothesis to be tested will be for primary endpoint MADRS change from baseline to endpoint, then change from baseline in CGI-SS, followed by time to treatment failure in the NRX-101 and lurasidone groups.

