### **19.3 Conventions**

Study visit dates will be analyzed using the nominal visit instead of the actual visit date.

Means, mean changes, standard deviations, and ranges will be presented separately for each treatment group. These endpoints will be evaluated using a paired t-test and between study treatment groups using an unpaired t-test at each time; these p-values will be presented as descriptive statistics.

For continuous variables, the mean, standard deviation, minimum, median and maximum will be presented, together with the total number of observations and the number of missing and non-missing values.

For ordinal and categorical variables, absolute and relative frequencies will be reported. Relative frequencies will be based on all observations and reported as percentages. Unless otherwise specified, percentages will be based on the number of participants with data and will not be calculated for missing categories.

Adverse events, medical histories, and concomitant medications will be reported on a patient and an event basis. Percentages will be calculated using the number of participants in the Safety population analysis set as the denominator.

All hypotheses will be tested at 5 percent (final analysis) level of significance using a two-sided test unless otherwise specified.

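### SAP 16.1 claims Type 1 error control for all efficacy endpoints, but the only usable testing order covers three and leaves five further superiority hypotheses unordered at 5%

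*SAP*

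**What the plan says.** SAP 16.1 opens with the purpose, "In order to preserve the Type 1 error associated with multiple endpoints (per FDA guidance", and continues that "all efficacy endpoints will be evaluated in this pre-defined order: (1) MADRS through Week 6". Nothing follows item (1) except a remark that each comparison rests on a hypothesis test. Protocol 16.3.1 has the same text.

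SAP 18.3 gives a fuller rule. It says "The secondary efficacy hypotheses will also be evaluated using a hierarchical testing strategy", continuing while two-sided p is below 0.05. The sequence starts with the MADRS primary endpoint, "then change from baseline in CGI-SS, followed by time to treatment failure in the NRX-101 and lurasidone groups". No endpoint is named after that. Protocol 16.6.2 agrees.

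SAP 16.3 formally states two secondary hypotheses, CGI-SS and time to treatment failure. SAP 11.2 lists the same two as the secondary endpoints, and 11.3 puts the others under an additional heading. SAP 17.1.2 calls most of those others additional secondary endpoints.

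SAP 7.2 has eight bullets under secondary objectives, each worded as a test of superiority. For example, NRX-101 is to be tested as "superior to standard of care (lurasidone) in reducing suicidal ideation (MADRS item 10").

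SAP 19.3 sets the level: "All hypotheses will be tested at 5 percent (final analysis) level of significance using a two-sided test unless otherwise specified".

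**The concern.** The error-control statement in 16.1 covers every efficacy endpoint, but the procedure that would deliver it covers three. For the remaining efficacy hypotheses, a reader of 7.2 together with 19.3 finds a superiority test at two-sided 5% and no rule on when that test may be interpreted.

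This matters most if the primary comparison fails. Under 18.3, CGI-SS and time to treatment failure could then not be tested. Nothing comparable holds back MADRS item 10, Day 14 MADRS, the SIBAT Module 7 items or the two subgroups.

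SIBAT is the clearest case. SAP 9.2 describes the CGI suicidality scales as ratings from SIBAT Module 7, and Protocol Appendix 2 lists the CGI suicidality severity instrument under that module. SAP 17.1.2 then lists each Module 7 item, including severity of suicidality, as a further endpoint. The plan therefore gates CGI-SS while leaving closely overlapping ratings open at 5%. A significant result on one of them could be presented as demonstrated superiority, citing a Type 1 error statement that does not protect it.

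**Working it through.** **1. The plan's own figures.** SAP 18.2: 37 per group, effect size 0.66, two-sided 5%, 80% power.
- Effect size: 8.85 / 13.4 = 0.660.
- Power from the noncentral t distribution with 72 degrees of freedom and noncentrality 0.66 × √(37/2): 80.0%.
- Critical effect size: t(0.975, 72) × √(2/37) = 0.463, against 0.462 stated.

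SAP 16.3, time to treatment failure: hazard ratio 0.421 with 80% power; 0.545 reaches p = 0.05.
- Events by the Schoenfeld formula: 4 × (1.96 + 0.84)² / (ln 0.421)² gives 42 after rounding up.
- Critical hazard ratio with 42 events: exp(−1.96 × 2/√42) = 0.546, against 0.545 stated.

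Both figures reproduce, and both use the full two-sided 5%. That is legitimate in a fixed sequence, so the three ordered endpoints raise no problem.

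**2. Which efficacy hypotheses lie outside the sequence.** SAP 7.2, bullet by bullet:

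| Hypothesis in SAP 7.2 | Place in SAP 18.3 |
|---|---|
| MADRS item 10 | none |
| Day 14 MADRS total | none |
| SIBAT Module 7 | none |
| CGI-SS | step 2 |
| Time to treatment failure | step 3 |
| Approved-medication subgroup, drugs named | none |
| Approved-medication subgroup, drugs not named | none (repeats the row above) |
| 5-HT2A subgroup | none |

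Eight bullets − 2 in the sequence = 6; less 1 duplicate = 5 distinct hypotheses.

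**3. Chance of at least one false positive among the five, all nulls true.**
- Independent tests: 1 − 0.95⁵ = 1 − 0.774 = 22.6%.
- Correlated tests: the documents give no correlations, so a common correlation ρ is assumed. Each statistic is √ρ·C + √(1−ρ)·E, with C shared and E separate standard normals, and is called significant if its absolute value exceeds 1.96 (400,000 draws):

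| Assumed ρ | At least one of five |
|---|---|
| 0.3 | 21.0% |
| 0.5 | 18.3% |
| 0.7 | 14.9% |
| 0.9 | 10.1% |

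These count errors in either direction. Counting only errors in favour of NRX-101, the independent figure is 1 − 0.975⁵ = 11.9%, against 2.5% for a single test.

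**4. Whether another section closes the gap.**
- SAP 19.3 calls the by-visit t-test p-values descriptive.
- SAP 7.3 only displays MADRS items and factors.
- The SAP synopsis tags remission from suicidality as exploratory.

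None of these labels covers the five hypotheses as a group. The rule that SAP methods override the protocol (SAP 13, Protocol 16) does not help, because both documents carry the same one-item sentence.

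**The case against.** The strongest reply is that the confirmatory family is already clear. SAP 16.3 and 11.2 name only CGI-SS and time to treatment failure, and 18.3 orders exactly those after MADRS. Protocol 7.2 and 7.3 likewise separate key from additional secondary objectives. On this reading 16.1 is clumsy drafting, and an endpoint absent from every order cannot credibly borrow its protection. Much of this stands: no conclusion on the primary endpoint, CGI-SS or time to treatment failure is affected. It does not remove the mismatch. SAP 7.2 merges the protocol's two tiers into one list of superiority tests, and 16.1 says all.

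Independence is also implausible. Item 10 is part of the MADRS total, Day 14 MADRS is the same scale in the same patients, the subgroups overlap, and SIBAT overlaps CGI-SS. That is fair, and it is why a range is shown.

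A reader might go further and add the four safety objectives in SAP 7.4. That gives ten bullets and 1 − 0.95¹⁰ = 40.1%. The documents do not support that figure as a measure of this problem. The 16.1 statement concerns efficacy endpoints, the SAP classes C-SSRS as a safety endpoint, and the ten include the duplicated subgroup bullet.

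A reader might also infer that 7.2, which places CGI-SS fourth and time to treatment failure fifth, sets a rival testing order. It does not: it is an unnumbered list of objectives and says nothing about sequence.

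**Conclusion.** The point stands as a mismatch between a stated error-control property and the procedure that delivers it. MADRS, CGI-SS and time to treatment failure are properly controlled at 5% by the 18.3 sequence. Five distinct efficacy hypotheses in SAP 7.2 are worded as superiority tests at 5% with neither a position nor a nominal label, so the claim in 16.1 is untrue for them.

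The size is 22.6% under independence and about 18% at a common correlation of 0.5, falling to about 10% at 0.9. These figures assume that all five nulls are true, that each hypothesis is tested once at two-sided 5%, and that the correlation is common to all pairs; the correlation values are assumptions. SIBAT Module 7 counts as one test here. SAP 17.1.2 names four ratings, which would make eight tests, but ratings within one module are where independence is hardest to defend, so no larger figure is claimed.

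The sample size and the primary analysis are unaffected. What changes is which results the trial may call confirmed.

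**What to change.** 1. In SAP 16.1 and Protocol 16.3.1, replace the one-item order with the sequence in SAP 18.3: MADRS, then CGI-SS, then time to treatment failure.
2. Limit the Type 1 error statement to those three endpoints.
3. In SAP 19.3, state that all other efficacy and safety comparisons are reported with nominal, descriptive p-values.
4. Align the objectives in SAP 7.2 and 7.4 and Protocol 7.3 and 7.4 with this, and remove the repeated approved-medication bullet from SAP 7.2. Changing the SAP objectives alone would create a new mismatch with the protocol.

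The cost is text edits in both documents, with no change to data collection, sample size or the primary analysis. The sponsor gives up confirmatory superiority claims on anything outside the three steps.
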